APPENDIX B. Operational Definition

INA 102 Version 5.0 10/02/2017

		10/02/2			
Monoresistance TB	By the result of Drug susceptibility test (DST)	DST result positive resistant to one of 1 st line TB drug other than rifampicin			
Polydrug resistance TB	By the result of Drug susceptibility test (DST)	DST result positive resistant to more than one of 1 st line TB drugs, in addition to combination of isoniazid and rifampicin			
Extensive drug resistance TB	By the result of Drug susceptibility test (DST)	DST result positive resistant to any fluoroquinolone and to at least one of three second-line injectable drugs (capreomycin, kanamycin and amikacin), in addition to multidrug resistance.			
Treatment outcome DS-TB					
Cured	Attending TB team report	Smear or culture negative in the last month of treatment and on at least one previous occasion			
Completed treatment	Attending TB team report	Completed treatment without evidence of failure but with no records to show that sputum smear or culture negative in the last month of treatment and on at least one previous occasion were negative, either because tests were not done or results are unavailable			
Died	Attending TB team report	Died from any cause during treatment			
Failed	Attending TB team report	Sputum smear or culture is positive at month 5 or later during treatment			
Loss to follow up	Attending TB team report	Did not start treatment or treatment was interrupted for two consecutive months or more			
Not evaluated	Attending TB team report	No treatment outcome is assigned. This include cases 'transferred out' to another treatment unit as well as cases for whom the treatment outcome is unknown.			
Successfully treated	Attending TB team report	The sum of cured and completed treatment.			

Treatment outcome MDR	-TB	10/02/2
Cured	Attending TB team report	Treatment completed as recommended by the national policy without evidence of failure AND three or more consecutive cultures taken at least 30 days apart are negative after the intensive phase.
Completed treatment	Attending TB team report	Treatment completed as recommended by the national policy without evidence of failure BUT no record that three or more consecutive cultures taken at least 30 days apart are negative after the intensive phase.
Failed	Attending TB team report	 Treatment terminated or need for permanent regimen change at least two anti-TB drugs because of: Lack of conversion at the end of intensive phase; or Bacteriologocial reversion in the continuation phase after conversion to negative; or Evidence of additional acquired resistance to fluoroquinolones or second-line injectable drugs; or Adverse drug reactions
Died	Attending TB team report	Died for any reason during course of treatment
Loss to follow up	Attending TB team report	Treatment was interrupted for two consecutive months or more.
Not evaluated	Attending TB team report	No treatment outcome is assigned. This include cases 'transferred out' to another treatment unit as well as cases for whom the treatment outcome is unknown.
Treatment success	Attending TB team report	The sum of Cured and completed treatment.

Demographics						
Age	Patient report	Last birthday				
Sex	Patient report	male and female				
Patient's history						
TB close contact	Patient report	Living in a same house with person who has TB				
Smoking habit	Patient report	Smoking status of participants				
Treatment seeking behavior	Patient report	History of health facility that been visited for treating these TB symptoms				
Co Morbidities						
HIV	Clinical and laboratory evaluation support HIV evidence	Positive result of HIV test				
Diabetes mellitus	Clinical and laboratory evaluation support diabetes evidence glucose test according to site SoC	Positive result of diabetes				
Symptoms	Patient report	Presence of TB symptoms from previous visit to current visit				
Nutritional status	BMI calculation based on data of Height and weight	< 18.5				
Treatment regiment	Source documents	Regiment of anti TB drugs given to the patients according to SoC				
Compliance	Patient report or blister count	Percentage of scheduled medication minus any medication left in the blister or based on patient report				

REFERENCES

1. World Health Organization W. Global Tuberculosis Control, Surveillance, Planning and Financing. Geneve: 2006.

2. World Health Organization W. Global Tuberculosis Control 2010. Geneve: 2010.

3. World Health Organization W. Global Tuberculosis Report 2016. Geneva: World Health Organization; 2016.

4. Departemen Kesehatan Republik Indonesia. Pedoman Nasional Penanggulangan Tuberkulosis. Jakarta2007.

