4.5 Inclusion and Exclusion Criteria

The following inclusion and exclusion criteria are used when determining eligibility patients into the study:

- 4.5.1 Inclusion Criteria
 - Patients suspected of having pulmonary TB
 - Cough ≥ 2 weeks
 - At least one other TB clinical symptom
 - Fever
 - Unexplained weight loss
 - Loss of appetite
 - Hemoptysis
 - Shortness of breath
 - Chest pain
 - Night sweats
 - Fatigue
 - Suggestive TB on chest x-ray based on pulmonologist or internist consultant of pulmonology opinion
 - Age \geq 18 years' old
 - Willing to be treated or evaluated at study site
 - Willing to have specimens stored for use in future studies
 - Patient denies having TB treatment for more than 7 days in the last 1 month (30 days).
- 4.5.2 Exclusion Criteria

Pregnancy or any serious condition includes, but not limited to, liver disease, chronic kidney disease, and psychiatric illness that might interfere with study compliance (based on the clinician judgment). In order to assess participant's pregnancy status, the attending clinician will ask the participant's first day of last menstrual period. The

final decision about participant's pregnancy status will be up to the attending clinician..

- 4.5.3 End of study criteria
 - Study completion (six months after end of treatment or six months after month 24th visit).
 - Participant desires to leave study or withdraw consent.
 - No sputum specimen for the examinations of AFB, Gene Xpert, and culture at baseline and enrollment visit.
 - No longer treated as TB patients.
 - Treatment interruption of two months or greater.
 - Death
 - Transfer to other health facility where follow up/evaluation is no longer possible.
 - Based on investigator's discretion it is in the participant's best interest to be discontinued from the study.
 - Participants who cannot be reached to complete the 6 months' post treatment by phone or direct visit.
 - Termination of study

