4.6 Instruments and Data Collection'

The following instruments and data collection methods will be used in this study. Further information may be found in protocol sections 4.6.2-4.6.5.

- 4.6.1 Instruments:
 - a. Forms
 - i. Informed consent
 - ii. Source documents
 - iii. Case report forms (CRFs)
 - iv. Screening Log
 - v. Enrollment Log
 - b. Databases
 - i. OpenClinica

ii. INA-RESPOND specimen database

- c. INA-RESPOND portal
- 4.6.2 Eligibility determination and enrollment:

Enrollment and baseline visit (visit 1)

Potential participants will be referred by physicians at participating hospitals.

Following referral, research assistant will check the eligibility criteria. Thus, the potential participant will be offered information on the study. If the patient agrees, he/she will sign the informed consent document and will be considered enrolled in the study. All baseline procedures should be done in five working days, although the result may come later. Enrollment day is considered as Day 0.

Demography, clinical data, and physical examination results including body weight and height will be obtained. The initial data collection will take time about 30-60 minutes.

Participant should bring enough sputum that can be considered eligible for AFB, Xpert MTB/RIF, and culture examination. Sputum induction by inhalation medicine will be considered for participants that have difficulty to produce sputum according to site SoC. The remaining sputum will be stored for TB related future testing. Participant who cannot provide enough sputum for those examinations will be considered as end of study and stop following the study procedures.

20 cc blood will be drawn for assessment of comorbidities (HIV test and HbA1c), for other examinations needed either for study or for SoC. Such as Hb, ureum, creatinine, AST, and ALT. Left over specimen will be used for future TB related examinations and repository. Less blood volume because unanticipated problem related to blood draw such as collapsing vein would not be considered as protocol deviation. 10 cc of urine will also be collected and stored for future TB related tests. Saliva will also be collected for storage.

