- 5) To compare the sensitivity and specificity of AFB and Xpert MTB/RIF relative

to culture result. Sensitivity and specificity will be estimated along with 97.5% confidence intervals. McNemar's statistic will test whether the sensitivity and specificity differ between AFB and Xpert MTB/RIF.

6) To estimate sensitivity and specificity of Rif susceptibility results in Xpert MTB/RIF against result in DST as gold standard along with 97.5% confidence intervals.

More specific plans for these analyses will be developed prior to the start of enrollment, and the plans may be adjusted during the course of the study.

Interim Analyses

Amongst presumptive new TB cases, we estimate that 25% will have confirmed TB, while amongst presumptive previously treated cases, we estimate that 70% will have confirmed TB. In order to ensure adequate numbers of TB cases, the accuracy of these estimates will be evaluated at 6 and 12 months after the study commences. Because of the expected two months waiting period for culture results, earlier looks at the data may not be informative.

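### Appendix B labels a drug-susceptible participant who dies before starting treatment as lost to follow-up, and handles the same death differently in MDR-TB

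*Combined protocol and SAP*

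**What the plan says.** Appendix B has one outcome table for DS-TB and one for MDR-TB. For DS-TB, Died is "Died from any cause during treatment" and Loss to follow up is "Did not start treatment or treatment was interrupted for two consecutive months or more". For MDR-TB, Died is "Died for any reason during course of treatment" and Loss to follow up is "Treatment was interrupted for two consecutive months or more", with no clause for never starting. Both tables have a residual label, Not evaluated, for which "No treatment outcome is assigned".

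Observation begins before treatment is certain. Under 4.6.2 a willing patient is a presumptive case when "he/she will sign the informed consent document and will be considered enrolled in the study", and results may come later.

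Sections 4.5.3 and 4.6.6 list death as its own reason for end of study, separate from "Treatment interruption of two months or greater". Section 4.6.6 restricts the interruption reason to people who had already begun treatment, and has the final treatment outcome determined at end of study.

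Section 4.7.2 uses the outcomes three times: item 1 estimates the proportions in five categories by susceptibility pattern, item 2 models treatment success, and item 3 models loss to follow-up against the other outcomes. The Research Summary (Study Design) says that participants given a TB regimen are the ones followed for outcome.

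**The concern.** A death and a default are different events with different causes. The DS-TB rule merges them for anyone who dies after consent but before the first dose. The proportion died and the proportion lost to follow-up are both named secondary results, so one is too low and the other too high by the same number of people. In item 3 those deaths become interruption events, so a characteristic that predicts early death can appear to predict default. The same person would be a death in the disposition data and lost to follow-up in the outcome table, with no rule saying which prevails. Because the MDR-TB table has no never-started clause, it sends the equivalent death elsewhere, and the two outcome tables are not built in the same way.

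**Working it through.** **1. Where each death goes, read literally from Appendix B**

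| Time of death | DS-TB | MDR-TB |
|---|---|---|
| Before any TB treatment | Not Died; meets the never-started clause, so Loss to follow up | Not Died; no interruption has occurred, so only Not evaluated is left |
| While on a TB regimen | Died | Died (the wording does not require an MDR regimen) |

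Nothing elsewhere in the document moves the first row into Died. Sputum is taken at baseline, so a participant who dies early can still be classed as DS-TB or MDR-TB when the culture and drug susceptibility test (DST) are read.

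**2. What each analysis in 4.7.2 then does with a pre-treatment death**

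| Item | DS-TB | MDR-TB |
|---|---|---|
| 1, outcome proportions | Counted as lost to follow-up | In none of the five categories |
| 2, success model | Non-success under either label | On neither side of the comparison |
| 3, interruption model | Counted as an event | Not an event, and without an assigned outcome |

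**3. Size: illustration only**

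The plan gives no mortality or loss-to-follow-up figure to reproduce. Its enrolment figure does reproduce: 250/0.25 = 1,000 and 250/0.70 = 357, total 1,357, giving 500 confirmed cases. I use n = 500. All rates below are assumptions: 5% die on treatment, 10% are truly lost to follow-up, and 1%, 2% or 5% die before treatment, all handled by the DS-TB rule. Intervals are exact 95%.

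- Died as written: 25/500 = 5.0% (3.3 to 7.3).
- Died with pre-treatment deaths included: 30/500 = 6.0% (4.1 to 8.5), 35/500 = 7.0% (4.9 to 9.6), 50/500 = 10.0% (7.5 to 13.0).
- Share of deaths missed: 5/30 = 17%, 10/35 = 29%, 25/50 = 50%.
- Reported loss to follow-up: (50 + 5)/500 = 11%, (50 + 10)/500 = 12%, (50 + 25)/500 = 15%, against a true 10%.
- Share of item 3 events that are deaths: 5/55 = 9%, 10/60 = 17%, 25/75 = 33%.

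If on-treatment mortality is varied over 3% to 10% and pre-treatment mortality over 1% to 5%, the shortfall in Died equals the pre-treatment proportion, 1 to 5 percentage points. The share of deaths missed runs from 1/11 = 9% to 5/8 = 63%.

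**4. Dependence on the denominator**

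If only treated participants are counted, as the Research Summary suggests, the 2% case gives 25/(500 − 10) = 25/490 = 5.1% instead of 5.0%. On-treatment mortality is then nearly unchanged, but the ten pre-treatment deaths appear nowhere in the outcome table.

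**The case against.** The strongest defence is that these are treatment outcomes. If the target population is people who started treatment, a death before treatment lies outside it, and the proportion died is not too low for what it estimates. That would stand if the plan said so consistently. It does not: the Research Summary points to treated participants, while the DS-TB table gives never-starters an outcome. Once they are in the table, a dead never-starter needs the right label.

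Three further objections have force.

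- The deaths are not lost to the study. Disposition records them, so they can be recovered if the plan says to use them.
- In item 2 a DS-TB death is non-success under either label, so the success model is unaffected for DS-TB.
- Item 3 includes regimen and compliance among its factors. A never-starter has neither and would drop out of a complete-case model that contains them. The misclassified deaths would still enter any model without those factors, and the plan does not say how missing covariates are handled.

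A reader might go further and infer that the omission is larger in MDR-TB, so that mortality by resistance is biased in a known direction. The documents do not support this. The MDR-TB definition refers to a course of treatment, not to MDR treatment, so a participant who dies on any TB regimen before the DST result may already count as died. The passage beginning "Because of the expected two months waiting period for culture results" explains the timing of the interim checks. It does not show that treatment waits for culture: AFB and Xpert are baseline tests in Appendix A, and Appendix B also allows a clinical diagnosis.

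Nor does the size of the MDR group supply an effect. At the plan's proportions, and assuming DST for all, about 250 × 12% + 250 × 1.9% = 34.75 MDR cases are expected, so one participant weighs 1/34.75 = 2.9 percentage points. That is the weight of any one person in the group; the documents give no number of such deaths.

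**Conclusion.** The point holds as a defect in a stated rule. As written, a DS-TB participant who dies between enrolment and treatment start is reported as lost to follow-up and is an event in item 3. An MDR-TB participant who dies without any TB treatment falls into Not evaluated, outside the five reported categories. Secondary objectives are affected; the primary MDR proportion is not.

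The size depends entirely on how many participants die before treatment, which the documents do not give. The 1 to 5 point shortfall reflects the assumed rates and is not an estimate for this study. Neither the size nor the direction of any effect on the contrast between drug-susceptible and drug-resistant groups can be derived. The conclusion assumes that Appendix B is applied literally and that the participant has a DST result. DS-TB is defined by DST, so someone who dies with no result belongs to neither table.

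**What to change.** 1. In both outcome tables of Appendix B, define Died as death from any cause after enrolment and before or during treatment, with precedence over Loss to follow up and Not evaluated.
2. Report pre-treatment deaths on a separate line, so that on-treatment mortality stays visible.
3. In 4.7.2 item 3, state that a pre-treatment death is not an interruption event.
4. State the denominator for the outcome proportions, and reconcile the Research Summary, which follows treated participants, with the never-started clause in the DS-TB table.
5. Confirm that the dates of death and of treatment start are captured. Appendix A does not list either. If they are missing, two date fields are needed on the case report form.

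The cost is wording in Appendix B and 4.7.2 and one extra table row, with no added patient procedures. The downside is that reported mortality may be slightly higher; the separate line lets a reader recover the on-treatment figure.

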3. OBJECTIVES

3.2 Primary Objective

To estimate the proportion of MDR TB amongst new and previously treated TB cases.

- 3.3 Secondary Objective
 - To evaluate accuracy of clinical diagnosis by comparing clinically defined TB

to laboratory confirmed TB.

- To compare AFB and Xpert MTB/RIF as TB diagnostic tests against culture result.
- To estimate the sensitivity and specificity of Xpert MTB/RIF in detecting Rif susceptibility against Drug Susceptibility Test (DST).
- To estimate the proportion of cured, completed, failed, died and lost to follow up as treatment outcomes in drug susceptible TB (DS-TB) cases and drug resistant TB (DR-TB) cases.
- To evaluate the association of treatment success (cured or completed) with the following data:
 - 1. Demographics (age, sex)
 - 2. TB contact history
 - 3. Smoking habit
 - 4. Treatment seeking behavior
 - 5. Co-morbidities (HIV, DM, cancer)
 - 6. Primary and secondary drug resistance
 - 7. Symptoms
 - 8. Cavitary disease
 - 9. Nutritional status
 - 10. Treatment regimens
 - 11. Patient reported compliance
 - 12. Numbers of bacteria by AFB test
 - 13. TB strains (e.g., Beijing)

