4.7.2 Analysis

This is an observational study to describe rates of MDR TB amongst new and previously treated TB cases in Indonesia. Risk factors for MDR will be evaluated as a secondary objective. Additional secondary objectives include a description of treatment outcomes (cure, failure, death, completed treatment) and evaluation of associated risk factors for poor outcome, comparison of diagnostic accuracy of AFB and Xpert MTB/RIF (relative to culture) and an estimation of Xpert MTB/RIF Rif susceptibility testing sensitivity and specificity relative to standard DST. Research objectives will be analyzed as described below.

Primary objective

 To estimate the rate of MDR-TB amongst new and retreated TB cases. Proportions of MDR will be estimated, along with exact 95% confidence intervals based on a binomial distribution. Case definitions of MDR, new and previously treated TB are provided in Appendix B.

Secondary objective

- To estimate treatment outcomes (cured, failed, died, treatment completion, and lost to follow up) according to susceptibility pattern. Proportions of participants within each category will be estimated along with confidence intervals. Definitions of treatment outcomes are provided in appendix B.
- 2) To evaluate risk/protective factors for treatment success (cured or completed treatment vs failed or died or loss to follow up). These factors include: demographics (age, sex), TB contact history, smoking habit, treatment seeking behavior, co-morbidities (HIV, DM), primary drug resistance, symptoms, no cavity in the lung, nutritional status, treatment regimens, compliance, numbers of bacteria and TB strains (e.g., Beijing). Logistic regression models will be used to describe associations of treatment success with these factors.
- 3) To evaluate risk/protective factors for treatment interruption (loss to follow up vs other treatment outcome). These factors include: demographics (age, sex), TB contact history, smoking habit, treatment seeking behavior, co-morbidities (HIV, DM, and other comorbidities), primary drug resistance, symptoms, cavity in the lung, nutritional status, treatment regimens, compliance, numbers of bacteria and TB strains (e.g., Beijing). Logistic regression models will be used to evaluate associations of treatment interruption with these risk factors.
- To compare clinically defined TB against laboratory confirmed TB. Accuracy will be estimated along with 97.5% confidence intervals.

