APPENDIX A. List of Study Procedures and Timeline

Procedures	BL	Mo1	Mo2	Mo3	Mo4	Mo5	Mo6	Mo7	Mo8	Mo9	Mo10	Mo12	Mo14	Mo16	Mo18	Mo20	Mo22	Mo24	6Mos Post Tx
Tiooodaloo								End of T	reatment							End of T	reatment	T	
Screening Log	ST ST																		
Enrollment Log	ST ST																		
Informed Consent	ST ST																		
Demography	SOC SOC																		
TB history & contact history	SOC SOC																		
Smoking Habit	ST ST																		
Treatment seeking	ST ST																		
HIV, DM, cancer comorbid data	ST,IA ST,IA	IA IA	IA IA	IA IA	IA IA	IA IA	IA IA	IA IA	IA IA	IA IA	IA IA	IA IA	IA IA	IA IA	IA IA	IA IA	IA IA	IA IA	
Symptoms	ST ST	ST ST	ST ST	ST ST	ST ST	ST ST	ST ST	ST ST	ST ST	ST ST	ST	ST ST							
Treatment Compliance		ST ST	ST ST	ST ST	ST ST	ST ST	ST ST	ST ST	ST ST	ST ST	ST								
Height	ST ST																		
Weight	SOC SOC	SOC SOC	SOC SOC	SOC SOC	SOC SOC	SOC SOC	SOC SOC		SOC SOC	SOC SOC	SOC	ST ST							
Chest X-Ray	SOC SOC						SOC	S				SOC			SOC			ST	ST ST
AFB	ST ST	ST IA	SOC IA	IA IA	IA	IA IA	IA	SC IA)C IA	IA	IA	IA	IA	IA	IA	IA	IA	IA	
Xpert MTB/RIF	ST SOC																		
Sputum Culture	ST ST	ST ST	ST ST	SOC	SOC	SOC	SOC	SOC		SOC	SOC	SOC	SOC	SOC	SOC	SOC	SOC	SOC	
1 st DST	ST SOC																		
2 nd DST	ST ST																		

INA 102

Version 5.0

10/02/2017

																	- 1	02,201	
Procedures	BL	Mo1	Mo2	Mo3	Mo4	Mo5	Mo6	Mo7	Mo8	Mo9	Mo10	Mo12	Mo14	Mo16	Mo18	Mo20	Mo22	Mo24	6Mos Post Tx
Procedures								End of T	reatment							End of T	reatment		Post IX
Hb, HbA1C,	ST																		
HIV exams	ST																		
Ureum, Creatinin,	IA																		
AST, ALT	SOC																		
Stored Whole	ST																		
Blood (DNA)	ST																		
Stored Plasma	ST	ST	ST					S	T										
	ST	ST	ST													S	Ţ		
Stored PBMC	ST	ST	ST					S	T										
	ST	ST	ST													S	Ţ		
Stored Serum	ST																		
	ST																		
Stored Paxgene	ST	ST	ST					S											
	ST	ST	ST													S	Ţ	1	
Stored Urine	ST	ST	ST					S											
	ST	ST	ST													S	Ţ		
Stored Sputum	ST	ST	ST					S	T										ļ
-	ST	ST	ST													S	Ţ		ļ
Stored Mtb	ST	ST	ST					S	T										
Isolate	ST	ST	ST													S	Ţ	1	ļ
Stored Saliva	ST							S	T										
Stored Sunta	ST															S	T		

*ST for HIV and DM, If available for other comorbidities

Blue	: Information for DS-TB
Red	: Information for MDR-TB
ST	: Procedure required by study that might be different from the site SoC

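### Appendix B ties diabetes to each site's own glucose testing and gives the study-required baseline HbA1c no role, cut-off or precedence, so diabetes status may be classified differently across the ten hospitals

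*Combined protocol and SAP*

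**What the plan says.** **The definition.** In Appendix B, under co-morbidities, the measurement entry for diabetes reads "Clinical and laboratory evaluation support diabetes evidence glucose test according to site SoC" and the operational definition reads "Positive result of diabetes". The only test named is a glucose test that follows each site's practice. There is no cut-off, no rule for known or treated diabetes, and no mention of HbA1c.

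**The measurement.** Section 4.6.2 provides at the baseline visit that "20 cc blood will be drawn for assessment of comorbidities (HIV test and HbA1c" will be obtained. Appendix A marks the row containing HbA1c as ST at baseline on both the DS-TB and the MDR-TB line. ST is explained as "Procedure required by study that might be different from the site SoC". The footnote on comorbidity data reads "ST for HIV and DM, If available for other comorbidities".

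**The use.** The secondary objectives list "Co-morbidities (HIV, DM, cancer") among the factors to be related to treatment success. Section 4.7.2 states: "Logistic regression models will be used to describe associations of treatment success with these factors". A parallel logistic analysis covers treatment interruption and also lists diabetes. Neither item names study site as a term, although ten hospitals contribute participants.

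**The concern.** The schedule requires one common diabetes test whatever the hospital normally does, but the definition of the analysis variable points back to what the hospital normally does. The HIV row of the same table has no such gap: there the criterion is a positive HIV test, and HIV testing is required by the study.

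Two consequences are possible. First, if site testing misses cases or labels some participants wrongly, the association of diabetes with treatment success and with interruption is pulled towards the null, provided the errors do not depend on outcome. Second, if the accuracy of testing differs between hospitals, recorded diabetes becomes partly a marker of hospital. If outcomes also differ between hospitals, a pooled model without site would attribute some of that difference to diabetes.

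The Background section singles out diabetes, together with HIV, as a comorbidity that worsens the TB burden and bears on treatment success. Readers are therefore likely to look for this estimate.

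**Working it through.** The documents give no diabetes prevalence, effect size, power or test accuracy for this analysis, so there is no planned figure to reproduce. The check has a textual part and an illustration.

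**1. The passages side by side**

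| Question | Section 4.6.2 and Appendix A | Appendix B |
|---|---|---|
| Which test? | HbA1c, baseline blood draw | Glucose test by site practice; HbA1c not named |
| Required by the study? | Yes (ST), both DS-TB and MDR-TB | Left to site practice |
| Cut-off? | None given | None given |
| Rule if results disagree? | None given | None given |

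No other section supplies a common definition.

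**2. Attenuation (illustration; every input is an assumption)**

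Assume true prevalence π = 0.15, unsuccessful treatment without diabetes p0 = 0.20, and true odds ratio 2.0. One sensitivity (se) and specificity (sp) applies to everyone, and errors are unrelated to outcome.

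- Odds without diabetes: 0.20/0.80 = 0.25. With diabetes: 0.50, so p1 = 0.50/1.50 = 0.333.
- Risk in those labelled diabetic: a = [π·se·p1 + (1−π)(1−sp)·p0] / [π·se + (1−π)(1−sp)].
- Risk in those labelled non-diabetic: b = [π(1−se)·p1 + (1−π)·sp·p0] / [π(1−se) + (1−π)·sp].
- Observed OR = [a/(1−a)] / [b/(1−b)].

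For se 0.6, sp 0.97:
- a = (0.09×0.333 + 0.0255×0.20)/0.1155 = 0.3039
- b = (0.06×0.333 + 0.8245×0.20)/0.8845 = 0.2090
- OR = (0.3039/0.6961)/(0.2090/0.7910) = 1.65

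| se | sp | a | b | Observed OR |
|---|---|---|---|---|
| 0.6 | 0.97 | 0.3039 | 0.2090 | 1.65 |
| 0.7 | 0.97 | 0.3073 | 0.2069 | 1.70 |
| 0.8 | 0.98 | 0.3168 | 0.2046 | 1.80 |

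The answer moves with the assumptions. The next table takes prevalence 10% to 30%, p0 20% to 30%, true OR 2.0, a two-sided 0.05 test, and all 500 confirmed cases having an outcome.

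| se | sp | Observed OR | Power |
|---|---|---|---|
| 1 | 1 | 2.00 | 0.58–0.93 |
| 0.90 | 0.98 | 1.78–1.88 | 0.46–0.87 |
| 0.60 | 0.98 | 1.66–1.73 | 0.31–0.64 |
| 0.60 | 0.90 | 1.29–1.48 | 0.16–0.45 |

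**3. Confounding by site (illustration; every input is an assumption)**

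The calculation in step 2 has no site in it, so it says nothing about differences between hospitals. For that, take two equal groups of sites, true prevalence 20% in both, and no true diabetes effect. Group 1 has se/sp 0.95/0.95 and group 2 has 0.50/0.99.

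- Apparent prevalence, group 1: 0.20×0.95 + 0.80×0.05 = 0.230.
- Apparent prevalence, group 2: 0.20×0.50 + 0.80×0.01 = 0.108.
- With failure 15% in group 1 and 35% in group 2, the risk in those labelled diabetic is (0.230×0.15 + 0.108×0.35)/0.338 = 0.2139. In those labelled non-diabetic it is (0.770×0.15 + 0.892×0.35)/1.662 = 0.2573. The pooled OR is 0.79.
- With the failure rates reversed, the pooled OR is 1.25.
- With failure 25% in both groups, the pooled OR is 1.00.

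A spurious association therefore needs outcomes that differ by site as well as testing that differs by site. Some patterns of unequal error produce almost none: se/sp of 0.90/0.98 against 0.60/0.90 gives 1.01 or 0.99 with the same 15% and 35% failure rates.

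**The case against.** The strongest defence is that the wording does not shut HbA1c out. An HbA1c result is a laboratory evaluation, and Section 4.6.2 says the blood is drawn for "assessment of comorbidities (HIV test and HbA1c"). On that reading HbA1c is already part of how diabetes is assessed. The reference to site glucose may also serve the follow-up visits, where comorbidity data are recorded if available and HbA1c is not scheduled. The table cell runs two phrases together without punctuation, so the relation between them is uncertain. This stands as far as it goes: one cannot say that HbA1c is excluded. But wording that admits either test without ranking them leaves the variable open, and the only test it names is the site-dependent one.

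A reader might infer that diabetes is in fact misclassified, and differently by hospital. The documents do not support that. They say nothing about which tests or cut-offs the hospitals use, so differing error is a risk and not a finding. Nor do the odds ratios in step 2 demonstrate it, since they rest wholly on assumed error common to all sites.

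Two further points stand. HbA1c is planned for all participants but not guaranteed, because a smaller blood volume is not a deviation. And Section 4.7.2 promises more specific analysis plans, where a rule could be set; those plans are not in the documents, so the gap remains in the text under review.

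**Conclusion.** The point holds as a gap in definition. Appendix B names site-dependent glucose testing and gives the study-required HbA1c no role, cut-off or precedence. Diabetes status may therefore differ in meaning across the ten hospitals. This could weaken its estimated association with treatment success and interruption. Confounding by site would require outcomes to differ by site too.

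The size cannot be computed from the documents. An observed odds ratio of about 1.65 to 1.80 for a true 2.0 is illustrative and depends on the assumed prevalence, baseline risk, sensitivity and specificity. Less accurate testing would pull it lower.

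Only the secondary risk-factor analyses are touched; the primary MDR proportions are not. This is a cheap improvement, not a threat to the study.

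**What to change.** In Appendix B, define baseline diabetes for analysis, at all sites, as either the study HbA1c at or above one cut-off fixed in advance by the sponsor, or a documented earlier diagnosis of diabetes or treatment for it. Then:

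- state that HbA1c prevails over site glucose when the two disagree;
- use site glucose only where HbA1c is missing;
- record the source of each classification (HbA1c, prior diagnosis or treatment, site glucose);
- include site in the logistic models for treatment success and treatment interruption. This addresses confounding by site but does not undo attenuation within a site, so it complements the common definition and does not replace it.

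The cost is a few lines of text and one source field, with no new procedure, because HbA1c is already scheduled. Settling it before analysis also avoids choosing between definitions once outcomes are known.

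There are three downsides. HbA1c can be shifted by anaemia, which can be examined because Hb is required at the same visit. Some HbA1c values may be missing, since reduced blood volume is allowed. The prior-diagnosis limb still depends partly on hospital records, so the definition becomes more uniform but not perfectly so.
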